Assess the effectiveness of different efficacious strategies to decrease the rate of major wound complications following abdominal surgery among high-risk individuals.

Hypotheses

1. Among high-risk patients undergoing abdominal surgery, the use of “small-bites” closure as opposed to “large-bites” closure will increase the proportion of patients who are free of major, chronic wound complications at 1-year post-operative.
2. Among high-risk patients undergoing abdominal surgery, the biologic tissue reinforcement of the suture line as opposed to no reinforcement will increase the proportion of patients who are free of major, chronic wound complications at 1-year post-operative.

Methods

This is a single-institution, 2x2 factorial randomized controlled trial assessing the effectiveness of known efficacious treatments (“small-bites” and tissue reinforcement) among high-risk patients undergoing midline laparotomy or laparoscopic-assisted surgery. [19] Laparoscopic-assisted abdominal surgery is defined as any surgery requiring an open incision in addition to laparoscopy to insert a hand (hand-assisted laparoscopy) or specimen extraction site ≥ 3 cm in

length. This length is chosen because any smaller incision will likely be closed with interrupted sutures rather than running sutures.

Table 1: 2x2 Factorial Design for Prevention of Major, Chronic Wound Complication [19]

		Randomization 1	
		Small-Bites	(Current Care) Large-Bites
Randomization 2	Mesh	Small-Bites Mesh	Large-Bites Mesh
	(Current Care) No Mesh	Small-Bites No Mesh	Large-Bites No Mesh

A 2x2 factorial trial design is utilized because it is more efficient (can assess two interventions simultaneously) and mimics real-world practice (e.g. adoption bundle therapies, adoption of multi-faceted interventions). In addition, the 2x2 factorial design remains novel, particularly among surgical literature that can improve profile of studies performed with this approach.

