Primary outcome will be proportion of patients at one year with a major chronic wound complication. Major chronic wound complications will include any persistent wound or infection at 1-year post-operative, fascial dehiscence, or fascial defect. Persistent wound or infection will include any enterocutaneous fistula, open wound, or symptomatic fluid collection. Fascial dehiscence or fascial defect will be defined as any defect noted on clinical assessment. Clinical assessment is clinical examination and demand-driven CT scan ordered based upon signs or symptoms including patient complaint of pain, bulge by patient report or physical exam, or wound complication. This represents current practice.[21] In addition, all patients will undergo

an ultrasound performed by a trained clinician to assess for any chronic, major wound complications at one year post-operative. Patients will also be followed for up to three years post-operative.

Secondary outcomes will include any Dindo-Clavien complications, surgical site infections, reoperations, operative duration, patient centered outcomes, surgeon perceptions, and cost analyses. Dindo-Clavien and surgical site infections have been defined.[20,22] Reoperation will be defined as any unplanned invasive procedure involving the fascia, mesh, or peritoneal cavity. Patient centered outcome based upon the modified Activities Assessment Scale and Euroqol-5D will be measured at 1 year and 3 years. Surgeon perceptions will include Likert type and open-ended questions assessing perception, barriers, and likelihood of utilizing the interventions outside of the trial. Cost will be calculated from the hospital's perspective by assessing charges for all patient visits, admissions, and procedures. These charges will be adjusted utilizing department-specific cost-to-charge ratios (CCR). The CCR are the ratios at the cost center level that hospitals are required to submit to Centers for Medicare and Medicaid Services annually (under the hospital's annual Medicare cost report). This will allow charges to be converted to cost by applying these CCRs to charges. Following state-of-the-art guidelines, cost will be discounted at an annual rate of 3%. The robustness of the results will be assessed by performing sensitivity analyses of plausible ranges for the project parameters and probabilistic sensitivity analysis. Follow-up schedule is provided in Table 2.

Table 2: Follow-up Schedule

Timing	Level of Care	Assessments	Reimbursements

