Based upon prior studies, it is estimated that the risk of a major, chronic wound complication in this population is at least 30% while either intervention would result in a decrease in relative risk by 30% (i.e. absolute risk reduction from 30% to 20%). The risk of complication at 1 year is the same with open or laparoscopic assisted surgery as shown in multiple prior studies. [1,2,26] Assuming an alpha of 0.05, beta of 0.20, and a dropout rate of 20%, a total of 192 300 patients would need to be enrolled and 154 patients randomized. Based upon our current surgical volume of nearly 6000 general surgical procedures performed each year and our track record of enrolling over 400 surgical patients in the past year for three other trials, we anticipate completing enrollment within one year. To encourage patient follow-up, all patients will be provided with up to a \$10 gift card at the one-year follow-up and \$20 at the three-year follow-up along with payments for their parking (\$10) at both one- and three-year visits. [23]

The primary outcome will be assessed as a categorical variable using a chi square test. In addition, analysis will be performed using a Cochran-Mantel-Haenszel method as well as a multivariate regression analysis accounting for the 2 randomizations and the stratification. Secondary outcomes will be assessed either chi-square or Kruskal-Wallis test.

Based upon traditional Frequentist assessment, if the effect size does not achieve “statistical significance” the conclusions risk being reported as a false negative. To address this potential risk, a more real-world, realistic analysis will be performed using a Bayesian analysis will also be performed. [24,25] The Bayesian models will take the same form as the Frequentist models and include the same covariates. Posterior point estimates, credible intervals, and probability of increase in proportion of patients without hernias or complications will be calculated. Similar models will be used for secondary outcomes. **If interactions or modifiers are identified, then this study will be underpowered and should be considered a pilot study to appropriately power future multi-center randomized controlled trials.**

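### The frequentist analysis of secondary outcomes is an unadjusted chi-square or Kruskal-Wallis test with no comparison groups, factor or stratum terms, or effect estimate; it should use the primary outcome's regression form

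*Combined protocol and SAP*

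**What the plan says.** The Methods section describes the design: "This is a single-institution, 2x2 factorial randomized controlled trial assessing the effectiveness of known efficacious treatments". Both hypotheses are factor-level contrasts: small against large bites, and biologic reinforcement against none. Randomization is stratified by surgical approach (laparoscopic or open).

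The Methods section also lists the secondary outcomes: "Secondary outcomes will include any Dindo-Clavien complications, surgical site infections, reoperations, operative duration, patient centered outcomes, surgeon perceptions, and cost analyses".

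In the Statistical analysis section, the primary outcome gets a chi-square test, a Cochran-Mantel-Haenszel analysis and "a multivariate regression analysis accounting for the 2 randomizations and the stratification". The complete frequentist plan for secondary outcomes is the sentence after that: "Secondary outcomes will be assessed either chi-square or Kruskal-Wallis test".

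The following paragraph adds a Bayesian analysis. "The Bayesian models will take the same form as the Frequentist models and include the same covariates". Its output is described as follows: "Posterior point estimates, credible intervals, and probability of increase in proportion of patients without hernias or complications will be calculated". It then says: "Similar models will be used for secondary outcomes".

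**The concern.** In a factorial trial each secondary result should say what small bites did and what mesh did. The secondary-outcome sentence does not secure this in the frequentist analysis, for three reasons.

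- **Comparison groups.** The sentence does not say whether tests are run on the two levels of each factor or across the four cells. Kruskal-Wallis is the rank test usually chosen for three or more groups, and Table 1 shows four cells. An analyst could therefore report four-cell p-values without departing from the plan.
- **Adjustment.** Neither test, used alone, carries a term for the other factor or for surgical approach.
- **Effect size.** Each test yields a p-value. No effect measure or confidence interval is named.

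At stake are the frequentist results for infection, complications and reoperation, and for function and quality of life, on which the Feasibility and Significance section says the trial will provide effectiveness data.

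**Working it through.** The plan gives no power figure for any secondary outcome, so there is none to reproduce. The checks below ask what the choice of comparison costs.

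**1. Four cells against two factor levels, in general**

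Inputs: two-sided alpha 0.05 (the plan gives 0.05 without stating sides), equal cells, one active factor, large-sample chi-square theory. The Kruskal-Wallis statistic has the same degrees of freedom.

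- Noncentrality for 80% power on 1 df: (1.960 + 0.842)² = 7.85.
- With only one factor active, the four-cell test has the same noncentrality but 3 df, so its critical value rises from 3.84 to 7.81.
- Power of the 3-df test at noncentrality 7.85: 0.645, or about 64%.
- The 3-df test needs noncentrality 10.90 for 80% power. The ratio 10.90 / 7.85 = 1.39 means about 39% more patients.

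**2. Illustration at the trial's size**

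No secondary event rates are given, so 30% and 20% are borrowed from the primary outcome as an assumption. The sizes are the 154 and 300 printed in the sample-size sentence, and 300 × 0.8 = 240 after the plan's 20% dropout. With N patients in all, the noncentrality is

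N × ((0.30 − 0.20)/2)² / (0.25 × 0.75).

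| N | Noncentrality | Per factor (1 df) | Four cells (3 df) |
|---|---|---|---|
| 154 | 2.05 | 30% | 20% |
| 240 | 3.20 | 43% | 29% |
| 300 | 4.00 | 52% | 36% |

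A simulation of Kruskal-Wallis (N = 240, normal data, assumed shift of 0.36 SD from one factor, 5,000 runs) rejected in 78% of runs on two groups and 62% on four.

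**3. Where the loss disappears**

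- *Per-factor tests.* On two groups, Kruskal-Wallis is the Wilcoxon-Mann-Whitney test. A numerical check gave p = 0.01389 for both (asymptotic, no continuity correction). No power is lost to extra degrees of freedom.
- *Both factors active.* With cell rates of 30%, 20%, 20% and 13.3%, the overall rate is 20.8% and the margins of one factor are 25% and 16.7%. At N = 240 the noncentrality is 2.53 on 1 df (power 36%) and 5.15 on 3 df (power 45%). The four-cell test rejects more often here, but it tests whether any cell differs and does not attribute the difference to small bites or to mesh.

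**4. Leaving out the stratum**

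For a continuous outcome, let R² be the share of variance explained by approach. In a balanced trial, including approach multiplies the residual variance by about 1 − R², so the unadjusted analysis behaves as if 1/(1 − R²) times as many patients were needed. The documents give no R², so these values are assumptions: 0 gives 1.00, 0.05 gives 1.05, 0.10 gives 1.11 and 0.20 gives 1.25. Operative duration is a plausible case of an outcome that differs by approach, but the documents do not say so.

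**5. Primary and secondary plans side by side**

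| | Primary, frequentist | Secondary, frequentist | Secondary, Bayesian |
|---|---|---|---|
| Both factors in a model | Yes | No | Yes, if it copies the primary model |
| Stratum | Yes | No | Yes, on the same reading |
| Effect estimate | Available from the regression | None | Posterior estimate and credible interval |

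**The case against.** The strongest reply is that the plan does provide factor-level estimates. "Similar models will be used for secondary outcomes" follows directly on the statement that the Bayesian models share the form and covariates of the frequentist ones, and the frequentist regression carries both randomizations and the stratification. This stands. A reader might infer that secondary outcomes get nothing but a test, or that the trial will not estimate the small-bites and mesh effects on them. The Bayesian paragraph contradicts both. It leaves the frequentist analysis unchanged, however, and the only regression it can copy is the one described for a categorical primary outcome, so the form for scores or duration is not stated.

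The second reply is that four-arm testing is an inference. This also stands. No groups are named, the hypotheses are marginal, and the primary outcome's chi-square test is named just as barely. The documents therefore do not support a statement that secondary results will be four-arm p-values or that the plan loses power. They support only that the wording permits this.

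Third, unadjusted per-factor tests in a randomized factorial trial are valid. The Methods section says approach was not chosen as a stratum from a belief that outcomes differ by it, and the Statistical analysis section assumes equal one-year complication risk by approach. Validity is conceded, and on that premise little is lost for complication outcomes. The premise does not extend to operative duration or cost.

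A further inference to resist concerns surgeon perceptions. The plan says: "Surgeon perceptions will include Likert type and open-ended questions assessing perception, barriers, and likelihood of utilizing the interventions outside of the trial". A reader might conclude that a few surgeons rate every technique, so that the answers are paired and the p-value wrong. The documents give neither the number of surgeons nor the unit or format of the survey, so this cannot be concluded.

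**Conclusion.** The point holds for the frequentist analysis of secondary outcomes. Unlike the primary outcome's regression, that analysis has no term for the other factor or for surgical approach, gives no effect estimate, and leaves open a four-cell test that answers neither hypothesis.

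The cost is conditional. The fall from 80% to about 64% assumes four-cell testing, one active factor, equal cells and two-sided 5% tests. Under per-factor testing it is nil. The precision lost by omitting the stratum depends on how far an outcome differs by approach, which the documents do not report.

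This is a change worth making because the better analysis is already written for the primary outcome. It does not show that the planned tests are invalid when run per factor.

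**What to change.** For each patient-level secondary outcome, replace the stand-alone chi-square or Kruskal-Wallis test with the primary outcome's regression form:

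- Include terms for small bites, mesh and surgical approach.
- Use logistic regression for binary outcomes such as infection and reoperation, and a suitable linear or ordinal model for scores and operative duration. Proportional-odds and mixed models are reasonable options here, not required corrections.
- Report the effect of each factor with a 95% CI.
- State that the Bayesian secondary models use the same form and covariates.
- Keep rank tests, run separately for each factor, as a sensitivity analysis.

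The cost is a few sentences of analysis text and a little programming, with no new data. The small downside is that the models add assumptions that rank tests avoid; the sensitivity analysis addresses this.

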Cost will be calculated by assessing charges for all patient visits, admissions, and procedures. These charges will be adjusted utilizing department-specific cost-to-charge ratio (CCR). The CCR are the ratios at the cost center level that hospitals are required to submit to Centers for Medicare and Medicaid Services annually (under the hospital’s annual Medicare cost report). This will allow charges to be converted to cost by applying these CCRs to charges. Following state-of-the-art guidelines, cost will be discounted at an annual rate of 3% for charges over 1 year. The robustness of the results will be assessed by performing sensitivity analyses of plausible ranges for the project parameters and probabilistic sensitivity analysis.

Feasibility and Significance

Our group has performed three prospective trials (2 randomized trial and one non-randomized trials), have completed enrollment for 2, and am on track to complete enrollment for the final study by March 2017. We have a strong track record of completing all projects that we have initiated ahead of schedule. This study will provide effectiveness data on the role of small bites

and biologic tissue reinforcement on the impact of patient satisfaction, quality of life, and function.

Budget

This study represents an effectiveness study of current practices and recommendations. At present, multiple societies recommend the use of mesh reinforcement and small-bites as best practices. [26] In addition, CMS has established a Current Procedural Code for tissue reinforcement for these cases.

The costs above our group's current practice are (1) ultrasounds performed at 1-year and (2) mesh. The department of surgery owns an ultrasound and the outcomes assessors will be trained on ultrasound of the abdominal wall course with the American College of Surgeons. [27] These cost of mesh have been offset by an investigator-initiated grant (all meshes will be donated by a biologic mesh company). The concerns for conflict of interest will be curbed by (1) the study will be overseen and performed by individuals with no direct benefit from this grant; an individual blinded to the allocations will assess the outcomes that also will receive no direct benefit from this grant.

References

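### Reoperation has no time window or denominator, and the only test named for it, chi-square, cannot use partial follow-up

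*Combined protocol and SAP*

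**What the plan says.** All of this is in the combined protocol and SAP.

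- **Outcome (Methods).** "Secondary outcomes will include any Dindo-Clavien complications, surgical site infections, reoperations, operative duration" and others. "Reoperation will be defined as any unplanned invasive procedure involving the fascia, mesh, or peritoneal cavity". The definition gives no time window, analysis time point or denominator. In the same paragraph the patient-centered scales are tied to fixed times ("will be measured at 1 year and 3 years"), and the primary outcome is fixed at one year.
- **Follow-up (Methods and Table 2).** "Patients will also be followed for up to three years post-operative", with visits at 1 month, 1 year and 3 years.
- **Test (Statistical analysis).** "Secondary outcomes will be assessed either chi-square or Kruskal-Wallis test". The Bayesian models for secondary outcomes follow the frequentist ones, so they bring in no time-to-event method. No rule for censoring, missing data or death as a competing event appears anywhere.
- **Loss (Statistical analysis).** The 20% dropout appears once, in the sample-size paragraph, with "154 patients randomized" given as the number randomized. It is not described as three-year loss and is not split by arm.

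**The concern.** Reoperations build up over time, and patients will be watched for different lengths of time. A chi-square reduces each patient to yes or no, and the plan does not say what value a patient lost at two months without a reoperation should take. There are two natural choices, and they err in opposite directions:

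- Dividing recorded reoperations by all randomized patients gives lost patients the same weight as those seen event-free for three years. The rate comes out too low.
- Dividing by patients with known three-year status (a recorded reoperation, or event-free to three years) drops the event-free time of those lost but keeps the reoperations recorded before loss. The rate comes out too high.

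Reoperation bears directly on the safety of adding mesh. Neither proportion estimates the three-year risk, and with the horizon and denominator open, either could be chosen after the data are seen. If retention also differs between the arms of a factor, part of any observed difference would come from follow-up and not from treatment.

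**Working it through.** The plan gives no figure for reoperation, so there is none to reproduce. The check shows what a crude three-year proportion would estimate.

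**Inputs**
- From the plan: follow-up to 3 years; 20% dropout, used here as loss by year 1; 154 randomized, so 154/2 = 77 per arm of each factor. The enrolment total is printed as two numbers, 192 and 300, so 300/2 = 150 per arm is shown too.
- Assumed: true three-year reoperation 20% in both arms with constant hazard; 35% loss by year 3; loss unrelated to reoperation; no deaths.

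**Formulas**
- Event hazard h = −ln(0.80)/3 = 0.0744 per year.
- Loss hazard in year 1: a = −ln(1 − L1). In years 1 to 3: b = −ln[(1 − L3)/(1 − L1)]/2.
- Recorded proportion R = h/(h+a) × [1 − e^−(h+a)] + e^−(h+a) × h/(h+b) × [1 − e^−2(h+b)].
- Seen event-free to three years: E = 0.80 × (1 − L3).
- Known-status proportion = R/(R + E).

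**Equal loss, 20% by year 1 and 35% by year 3**
- a = 0.2231, b = 0.1038.
- R = 0.0643 + 0.0929 = 0.157 (rounded), so 15.7% over all randomized patients.
- E = 0.80 × 0.65 = 0.520, and 0.157/(0.157 + 0.520) = 0.232, so about 23% over known status.
- The true value is 20%. Both arms shift alike, so the false difference is 0 and the test keeps its 5% level.

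**Unequal loss, same true rate**

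| Loss by year 1 / year 3 | Over all randomized | Over known status |
|---|---|---|
| 15% / 30% | 16.6% | 22.8% |
| 25% / 40% | 14.9% | 23.7% |
| Difference | 1.7 points | −0.9 points |

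For the all-randomized proportion, the standard error of the difference is √[2 × 0.157 × 0.843/n], which is 5.9 points at n = 77 and 4.2 points at n = 150. A false shift of 1.7 points raises two-sided type I error from 5% to about 5.9% and 6.8%. For the known-status proportion it is about 5.1% and 5.3%.

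**Wider imbalance.** A separate simulation took three-year true rates of 10% to 30%, loss of 10% against 30%, and loss either gradual or all at one month. With lost patients counted as event-free, the false difference was 1.1 to 5.8 points and type I error about 6% to 22%. Chi-square on known status gave 4.5% to 8.3%. A log-rank test with censoring stayed between 4.4% and 5.7% in every scenario simulated, with equal or unequal loss.

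**The case against.** The strongest reply is that the plan is silent here, not wrong, and that the harm is conditional.

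- **Lost patients counted as event-free.** A reader might infer that the plan does this. It names a test and no denominator, so the inference is not supported. This stands.
- **A false treatment difference.** A reader might infer that one will arise. It needs loss that differs by arm. The plan gives a single overall 20% and no sign of imbalance. With equal, uninformative loss the test keeps its level, and a relative risk of 0.70 stays at about 0.70. This stands.
- **Severe Dindo-Clavien events.** A reader might extend the point to grades 3 to 5. The secondary outcome is any Dindo-Clavien complication; those grades appear only as events for safety board review. There is no such comparative endpoint to re-analyse.
- **Mitigation.** Patients unlikely to return or to survive two years are excluded, and return visits are paid. Costing also draws on records ("Cost will be calculated by assessing charges for all patient visits, admissions, and procedures"), so a missed visit need not mean a missed reoperation. This lessens the problem. It does not supply a window or denominator, and costs are taken from the hospital's perspective, so reoperations elsewhere may go unseen.
- **A fixed one-year proportion.** With a stated denominator and a missing-data rule, this would remove the ambiguity and shrink the bias. Under the same assumptions the true one-year rate is 1 − e^−0.0744 = 7.2%. The crude values are 6.4% over all randomized and 0.0643/(0.0643 + 0.9283 × 0.80) = 8.0% over known status. That is a fair fallback, but it gives up the reoperations of years 1 to 3.

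**Conclusion.** The point holds in a limited form. The plan fixes no horizon, denominator or censoring rule for reoperation, and its only applicable test cannot use partial follow-up. A crude three-year proportion is off under either natural denominator: about 15.7% or about 23% for a true 20%, given the assumed constant hazard and 20%/35% loss. The comparison between arms is much less exposed. It is sound under equal loss. Under an assumed 15%/30% against 25%/40%, the all-randomized analysis shows about 1.7 points with none true and type I error of about 6 to 7%. The reoperation rate, the year-3 loss and any imbalance are assumptions, and larger distortions need larger imbalance than the documents suggest. The primary outcome is not affected. The change is worth making because a better method is available cheaply for an outcome that bears on mesh safety.

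**What to change.** Replace chi-square for reoperation with an analysis of time from abdominal closure to first reoperation, treating death as a competing event.

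- Report 1- and 3-year cumulative incidence (Aalen-Johansen) for each factor.
- Compare by a cause-specific Cox model with both factors, stratified by surgical approach, or by a Gray test for each factor that allows for the other factor and for approach.
- Censor at the last date to which reoperation status is actually known, under one rule for patients with and without events. If record searches pick up events after a missed visit while event-free patients are censored at their last visit, incidence is overstated. The rule should therefore say to what date the records were searched for everyone.

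The cost is SAP wording and slightly more analysis. Procedures and admissions are already being gathered for the cost outcome, so event dates should need no new visits. One limit remains: hospital records may miss reoperations at other hospitals, so patients should be asked about these at the 1- and 3-year visits.

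### The only frequentist test stated for cost is a rank test, which does not estimate the mean cost difference the hospital needs and can disagree with it

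*Combined protocol and SAP*

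**What the plan says.** The Methods section names the secondary outcomes: "Secondary outcomes will include any Dindo-Clavien complications, surgical site infections, reoperations, operative duration, patient centered outcomes, surgeon perceptions, and cost analyses". It takes cost from the hospital's perspective.

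The Statistical analysis section gives one frequentist rule for all of these outcomes: "Secondary outcomes will be assessed either chi-square or Kruskal-Wallis test". It then describes Bayesian models for the primary outcome, with the same form and covariates as the frequentist ones, and adds: "Similar models will be used for secondary outcomes". The outputs named are: "Posterior point estimates, credible intervals, and probability of increase in proportion of patients without hernias or complications will be calculated".

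The cost paragraph that closes the section covers measurement ("Cost will be calculated by assessing charges for all patient visits, admissions, and procedures"), conversion by cost-to-charge ratios, discounting ("cost will be discounted at an annual rate of 3% for charges over 1 year") and robustness ("sensitivity analyses of plausible ranges for the project parameters and probabilistic sensitivity analysis"). It does not say how cost is compared between arms.

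**The concern.** A hospital's budget effect is mean cost multiplied by the number of patients. Kruskal-Wallis does not address the mean. It asks whether patients on one side tend to rank higher than those on the other. The two questions can have different answers when an intervention adds a modest cost to nearly everyone and spares a few patients a large one. The rank test counts the many small increases and gives little weight to the size of the few savings.

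Two things are at stake. The cost conclusion could differ from the mean comparison in significance, and under some cost patterns in sign. In addition, a probabilistic sensitivity analysis needs an estimate with its uncertainty, and a Kruskal-Wallis p-value supplies neither.

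**Working it through.** The plan states no figure for cost, so there is none to reproduce.

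**Inputs from the documents.** The complication risk is 30% without and 20% with an intervention (Statistical analysis). For numbers per side of each randomization, 154 randomized gives 154/2 = 77. The sample-size sentence prints both 192 and 300 as enrolled; taking 300 with 20% dropout gives 300 × 0.8 / 2 = 120.

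**Inputs assumed.** All dollar amounts are assumptions. Write *a* for the cost the intervention adds to every patient and *C* for the cost of a complication.

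**Step 1: can ranks and means disagree?** Give every patient the same base cost, with *C* > *a*.

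- An intervention patient costs more than a control patient if neither has a complication (0.8 × 0.7 = 0.56) or if the intervention patient has one (0.20). Hence P(intervention dearer) = 0.56 + 0.20 = 0.76, whatever the values of *a* and *C*.
- The mean difference is *a* + 0.20*C* − 0.30*C* = *a* − 0.10*C*, a saving whenever *C* > 10*a*.
- With *a* = $2,000 and *C* = $40,000 the mean difference is 2,000 − 4,000 = −$2,000. The intervention saves money on average, yet the ranks say it costs more.

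**Step 2: how often, once base costs vary?** The simulation used a lognormal base cost with mean $15,000, a lognormal complication cost (log-SD 0.5), 77 or 120 per side, and a two-group Kruskal-Wallis test at two-sided 0.05.

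| *a* | *C* | True mean difference | Rank test significant for intervention dearer |
|---|---|---|---|
| $3,000 | $30,000 | 3,000 − 3,000 = $0 | about 10-29% |
| $2,500 | $40,000 | 2,500 − 4,000 = −$1,500 | about 5-14% |
| $1,000 | $40,000 | 1,000 − 4,000 = −$3,000 | about 1% or less |

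The high ends belong to 120 per side with a narrow base-cost spread (log-SD 0.35). At 120 per side with log-SD 0.6, the first two rows fall to about 13% and 6%. Repeat runs differ by up to about three percentage points. In the $0 row a t test on means rejects in about 5% of trials, both directions together.

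**Step 3: power when the added cost is small.** With *a* = $1,000 and *C* = $40,000, the rank test finds the true $3,000 saving in about 5-9% of trials, against about 10-19% for a comparison of means.

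**Step 4: two groups or four.** These directions apply to a two-group test on each randomization. Kruskal-Wallis across the four cells would be an omnibus test with no direction, would not use the factorial structure, and would still give no mean difference.

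**The case against.** Three objections have force.

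**The rank test is not the only analysis announced.** The Bayesian sentence extends covariate-adjusted models, with point estimates and credible intervals, to secondary outcomes. A reader might infer that cost gets nothing but a rank test and that no cost difference with an interval will be produced. The documents do not support that. What remains is that no likelihood, scale or estimand is given for cost, no frequentist cost model exists for the Bayesian one to mirror, and the only directional output named concerns a proportion.

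**The cost paragraph points to something other than ranks.** Ranks have no parameters to vary, so a probabilistic sensitivity analysis suggests that a model-based evaluation is intended. That is a fair reading of intent. But those analyses test the robustness of a result, and the paragraph does not define the result.

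**The reversal needs a real added cost.** The Budget section lists only the one-year ultrasound and the mesh as costs above current practice. The ultrasound is for all patients, so it does not differ by arm, and the meshes are donated. No added cost is listed for small bites; operating time could add one, but no figure is given. How mesh placement would be charged is not stated. The recorded added cost may therefore be small. This stands, and it rules out presenting a reversal as the expected result.

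A comparison of means is not powerful either: in the $1,500-saving scenario it is significant in the right direction in only about 8-10% of trials at 120 per side.

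**Conclusion.** The point holds in a limited form. The only frequentist test the plan states that fits a continuous cost is Kruskal-Wallis. It does not estimate mean cost and leaves the planned sensitivity analyses without a specified estimate. That part needs no dollar assumption.

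The size of the effect does depend on assumptions. Over the scenarios examined, a significant result in the wrong direction, or for a difference that does not exist, ranges from about 1% or less to about 29% of trials, according to the added cost, the complication cost, the base-cost spread and the number per side. A reader might infer from the upper figures that the cost conclusion is likely to have the wrong sign. The documents give no costs to support that, and donated mesh argues against a large added cost. If the added cost is small, the main consequence is lost power. The primary outcome is not affected.

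**What to change.** Exclude cost from the sentence that assigns secondary outcomes to chi-square or Kruskal-Wallis. In the cost paragraph, make the primary cost comparison the difference in arithmetic mean cost, with a 95% interval, for each randomization: small v large bites, and mesh v no mesh. Estimate it by linear regression with bootstrap intervals, or by a generalized linear model with the results reported as differences in marginal mean cost. Include both factors and the surgical-approach stratum. Carry this estimate and its uncertainty into the sensitivity analyses. If the Bayesian models are to cover cost, state their likelihood and scale. Any rank test on cost can remain as supplementary.

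This costs a few sentences in the plan and a little more analysis; no new data or patients are needed. The intervals will be wide because costs are skewed, and power for cost will be low. The report should say so.
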